1.0 INTRODUCTION

This document is a protocol for a human clinical investigation. The study is to be conducted according to US and international standards of Good Clinical Practice (GCP), Food and Drug Administration (FDA) Title 21 part 312 and International Conference on Harmonization (ICH) Guidelines, applicable government regulations and institutional research policies and procedures.

2.0 BACKGROUND

2.1 Acute Infectious Conjunctivitis

Acute infectious conjunctivitis (“pink eye”) is one of the most common and most contagious ocular infections in the US and the rest of the world. It is usually caused by either bacteria (both Gram-positive and Gram-negative) or more commonly, multiple serotypes of human adenovirus. In addition to the direct damage caused by the infection itself, the body’s stereotyped immune response often overwhelms the delicate structures of the eye and leads to secondary, often permanent, inflammatory damage. While some combination antibiotic/anti-inflammatory drugs have been useful for routine bacterial conjunctivitis, all are suffering from increasing antibiotic resistance, and are contraindicated in the case of suspected viral infection due to their propensity to worsen the duration and severity of viral infections.

2.2 MEDICAL NEED IN ACUTE INFECTIOUS CONJUNCTIVITIS

Clinical differentiation of bacterial and viral conjunctivitis has depended on clinical signs, symptoms and history^{1,2}. These factors are often accepted among practicing ophthalmologists as reliable indicators of etiology with little or no peer-reviewed literature substantiation. An evidence-based review by Rietveld *et al*³ reviewed several databases, including the Cochrane Controlled Trials Register, along with standard ophthalmology texts and concluded that there is no evidence that signs and symptoms definitively differentiate viral from bacterial conjunctivitis. This lack of ability to clinically determine viral versus bacterial, combined with the known high prevalence of viral infections requires that physicians suspect virus in every case of acute conjunctivitis.

Although exact numbers are difficult to determine, estimates from a national survey of outpatient health encounters^{4,9}, comparison with epidemiological surveys completed in other countries^{5,6,7} and studies of incidence in military recruits⁸ suggest that the number of cases of viral conjunctivitis may be as high as 15-20 million per year in the United States. Experts estimate the socioeconomic impact (in terms of lost work hours) from this disease is in the billions of US dollars. There is no FDA approved drug available to treat these cases: there are no antibiotics, anti-inflammatories or combination products FDA-approved for the treatment of viral conjunctivitis. This represents a massive unmet need in ophthalmology.

2.3 SCH1

SCH1 is a novel combination anti-infective / steroid eye drop with *in vitro* efficacy against many bacteria, yeasts, fungi and human adenovirus. The product contains two FDA-approved active pharmaceutical ingredients (Pred Forte, or prednisolone acetate 1%, application #017011, approved May 30, 1973; chlorhexidine gluconate, approved December 28, 1995). The combination is formulated as a 0.2% chlorhexidine 1% prednisolone acetate ophthalmic suspension. In preclinical evaluation, it demonstrated antimicrobial efficacy on contact with ocular isolates of *S.aureus*, *P. aeruginosa*, *E. coli*, *C. albicans*, and *A. brasiliensis*. A review of preclinical studies is provided in the investigators brochure.

2.4 Study Rationale

Acute infectious conjunctivitis is a leading cause of ocular morbidity, epidemic eye infection, lost productivity, patient discomfort and in some cases permanent visual compromise. The infectious agent is frequently viral in origin and frequently bacterial in origin with very little to reliably distinguish one from the other. Concomitant inflammatory damage often occurs and can lead to long term ocular morbidity. No current treatments are capable of treating both viruses and bacteria. Additionally no current combination antibiotic/steroid combinations can safely be administered in suspected viral infections. The objective of this study is to assess the efficacy of SCH1

as a first-line treatment for ocular inflammation and infection in the setting of an acute viral or bacterial conjunctivitis infection.

2.5 Dose Rationale

Each drop of SCH1 (approx. 80-110 microliters) contains 0.2% chlorhexidine gluconate and 1% prednisolone acetate. To adequately treat both the inflammatory and infectious components of acute conjunctivitis, frequent dosing is employed early in the course of infection which can be tapered rapidly as symptoms resolve. We will employ a regimen of 1 drop every two hours while awake in affected eyes on Day 1 followed by 1 drop four times a day for the remaining four days of treatment.

3.0 Objective

The objectives of this study are to evaluate the effectiveness of SCH1 in the treatment of infectious conjunctivitis.

4.0 Endpoints

4.1 Primary Endpoints

The primary endpoint will be the achievement of a clinical cure defined as a rating of 0/3 for bulbar conjunctival injection and 0/3 for conjunctival exudates/discharge or clinical success defined as an overall decrease by 3 in the sum of both scores.

4.2 Secondary Endpoint

Patients will keep a log and rate their symptoms on a pre-determined scale each of the 5 days of the study.

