Eligibility Criteria	
Inclusion Criteria
 
 • Conjunctivitis (as defined below) within 72 hours of initial ocular symptoms. • At least 18 years of age. • Subjects capable of understanding the purpose and risks of the study, and able to give informed consent. • Conjunctivitis diagnosis defined as presence of the two cardinal signs of acute conjunctivitis- 1) bulbar conjunctival injection and 2) conjunctival discharge/exudates. • A three-point rating scale (0=absent, 1=mild, 2=moderate, 3=severe) will be employed to grade conjunctival discharge/exudates. • All patients will require a rating of 1(mild) or greater for conjunctival discharge/exudates. • Patients will require a rating of 1 (mild) for bulbar conjunctival injection.
	
Exclusion Criteria
 
 • Conjunctivitis greater than 72 hours after initial ocular symptoms • Corneal ulcer, endophthalmitis, or any other confounding infection of the eye • Patients taking topical anti-inflammatory medications on a chronic basis • Known steroid glaucoma responders • Active herpes ocular infection • Pregnant women • Known allergy to chlorhexidine
Trial Design	This is a phase II single-center, prospective, placebo-controlled, randomized study of SCH1 in the treatment of acute infectious conjunctivitis. Study drug will be evaluated against vehicle.
Primary Endpoint	Clinical cure defined as rating of 0/3 for bulbar conjunctival injection and 0/3 for conjunctival exudates/discharge or clinical success defined as an overall decrease by 3 in the sum of both grades.

Secondary	
 Patients will keep a self log of symptom score each of the 5 days of the study
Number of Subjects	
 30 (15 per treatment arm)
Target Population	
 Patients with infectious conjunctivitis defined by bulbar conjunctival injection (rated at least 1 on 3 point grading scale) and conjunctival exudates / discharge (rated at least 1 on 3 point grading scale). Patients greater than one year of age. Patients of any race or ethnic group.
Length of Study	
Enrollment period: 12 months Treatment period: 5 days Overall duration: 6 months 5 days

Study Drug	
Subjects will be randomized to one of the following treatment arms: Treatment Arm A: SCH1 Treatment Arm B: Placebo (Vehicle only)

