Assessment of Safety	
 Incidence of SPK at day 1 Incidence of SPK at Day 5 Intraocular pressure at Day 5 
VA loss of 4 or greater lines on Snellen VA Chart

Interim Analysis and Safety Monitoring	
 Safety data will be reviewed by [name], Medical Monitor and Sponsor. A summary report of the safety points will be created every 3 months, as well as the end of the study, and reported to the IRB.
Statistical Analysis	
The statistical analysis will evaluate: 1) The overall clinical success rate defined as the percentage of study participants achieving a clinical cure by Day 5 or an overall decrease in the sum of both grades by 3; 2) Microbiological cure rate defined as the percentage of study participants who demonstrate elimination of pre-treatment pathogen(s) by the Day 5 TOC exam.
 
A statistical difference in clinical cure rate will be defined where the 95% confidence limit for the difference in the two study groups (SCH1 vs. Placebo) is greater than (+/-)15%.
 
All data will be examined employing an “Intent to Treat” analysis for all patients. Mean outcome variables in the two study groups will be compared. Statistical means between both study groups will be analyzed by both parametric and non-parametric tests to allow for deviations of data from normal distributions.

Schedule of Visits and Assessments

	Screen / Visit 1	Visit 2	Visit 3
	Day 1	Day 3	Day 5
General Exams			
Informed consent	x		
Inclusion/exclusion criteria	x		
Medical history	x		
Vital signs	x		x
Physical Exam	x		
Patient comfort exam	x	x	x
AE assessment	x	x	x
Current meds	x	x	x
Ophthalmic exams			
BCVA	x		x
Visual acuity	x	x	x
Anterior segment slit lamp exam and tonometry	x	x	x
Dilated fundus exam	x		x

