7.1 Screening Prior To Randomization

A screening examination is performed on the initial visit. Screening procedures will include:

- Informed consent

- Inclusion/exclusion criteria

- Complete medical history and demographic information

- Best corrected visual acuity

- Slit lamp examination and tonometry

- Graded assessment of conjunctival inflammation and cornea

- Dilated fundus examination or Optos Fundus photography

- Conjunctival culture swab (A pre-packaged swab (*Visufarma Adenoplus*) to obtain a viral culture from the eye)

Documentation of the subject's fulfillment of the entry criteria for all subjects considered for the study and subsequently included or excluded is to be completed by the Investigator or designee. Documentation of screening failure details will be recorded in the source documentation.

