7.2 Study Procedures/Assessments

The second visit has a +/- 1 day window. The third visit has a +/-1 day window.

Visit 1

Perform the following activities on Visit 1 (baseline)

- Review

- BCVA

- SLE and tonometry

- DFE

- Grading of injection / discharge

- Dispense study medication

Visit 2

Perform the following activities on Visit 2

- Record AEs

- Review of current medications

- Visual acuity

- SLE

- Grading of injection / discharge

Visit 3

Perform the following activities on Visit 3

- Record AEs

- Review of current medications

- Visual acuity

SLE
Grading of injection / discharge
DFE

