8.2 Study Drug Administration

The study drug is administered as one drop to the affected eye every two hours while awake on Day 1, four times per day while awake for Day 2 through Day 5. The drugs are administered by the patient.

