9.3 Other Assessments of Efficacy

Patients will keep a record of their own subjective symptom score from 1-5.

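### The only secondary endpoint, the 1-5 symptom self-log, has no specified pre-dose baseline; a Day 5 comparison stays unbiased but gives up precision that one Visit 1 item would secure.

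*Combined protocol and SAP*

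**What the plan says.** - **Endpoint.** Protocol section 4.2: "Patients will keep a log and rate their symptoms on a pre-determined scale each of the 5 days of the study". The synopsis, under its secondary heading, agrees and lists nothing else: "Patients will keep a self log of symptom score each of the 5 days of the study".
- **Scale.** Section 9.3 (Other Assessments of Efficacy): "Patients will keep a record of their own subjective symptom score from 1-5". No anchors and no time of day are given.
- **Dosing.** Section 8.2 has patients give themselves one drop "every two hours while awake on Day 1", then four drops a day on Days 2 to 5. Log days and dosing days therefore coincide.
- **Visit 1.** Section 7.1 includes "Graded assessment of conjunctival inflammation and cornea" but no symptom score. The baseline list in section 7.2 covers visual acuity, slit lamp and tonometry, fundus examination and grading of injection and discharge. It ends with "Dispense study medication" and also has no symptom score.
- **Schedule of Visits and Assessments.** A row labelled "Patient comfort exam" is marked at Days 1, 3 and 5. It is described nowhere else and is absent from sections 7.1 and 7.2.
- **Analysis.** The synopsis says that mean outcomes in the two groups will be compared by parametric and non-parametric tests. The SAP names no test, time point or baseline for the log.

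**The concern.** The clinical signs behind the primary endpoint are graded at Visit 1, in a list that ends with dispensing, so they have a pre-dose value. Nothing equivalent is specified for symptoms. Drops and log are both in the patient's hands. One patient may make the Day 1 entry before the first drop and another after several, and no instruction separates the two.

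Two things are at stake. First, with about 15 patients per arm, chance differences in starting symptoms can be sizeable, and a same-scale pre-dose score is the natural covariate to remove them. If it is not taken before the first drop, it cannot be recovered. Second, with no baseline defined, an analyst may later use the Day 1 entry as one, although it may already reflect treatment.

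**Working it through.** **1. The plan's own figure.** The SAP states 87% power for clinical cure, 20% against 80%, 15 per group, two-sided Fisher's exact test at 0.05. Full enumeration over two Binomial(15, p) arms gives 0.872, so the figure reproduces. It concerns the primary endpoint only. No power, SD or effect size is stated for the symptom log.

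**2. Is a pre-dose symptom score specified anywhere?**

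| Place | Symptom score? | Timed before the first drop? |
|---|---|---|
| 4.2, 9.3, synopsis (log) | Yes, daily, 1-5 | Not stated |
| 7.1 screening list | No | – |
| 7.2 Visit 1 list | No | – |
| Schedule, comfort exam on Day 1 | Content and scale undefined | Not stated; likely if done with the other Visit 1 examinations |

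No passage fixes one, and no passage rules one out.

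**3. Precision lost without a pre-dose covariate.**
- From the documents: n = 15 per arm (synopsis and SAP; section 11.0 speaks of 30 per group, which conflicts with these) and two-sided 0.05 (SAP).
- Assumed: a true Day 5 difference of d = 1 SD, and a correlation r between the pre-dose and Day 5 scores.

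Chance imbalance: the standard error of the between-arm difference in a baseline score is √(2/15) = 0.37 SD.

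Unadjusted t test: noncentrality d√(n/2) = 1 × √7.5 = 2.74 on 28 df, power 0.753.

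Adjusted for the pre-dose score: the residual SD is multiplied by √(1 − r²), so the noncentrality becomes 2.74/√(1 − r²) on 27 df. The equivalent unadjusted sample is 15/(1 − r²) per arm.

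| r | Noncentrality | Power, d = 1 | Equivalent n per arm | Power, d = 0.8 |
|---|---|---|---|---|
| none (unadjusted) | 2.74 | 75% | 15 | 56% |
| 0.3 | 2.87 | 79% | 16.5 | 60% |
| 0.5 | 3.16 | 86% | 20.0 | 68% |
| 0.7 | 3.83 | 96% | 29.4 | 84% |

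The noncentrality column is for d = 1. These are normal-theory figures applied to a five-point scale, so they are approximate.

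**4. What if someone used change from Day 1?** The plan does not call for this. Let f be the share of the Day 5 effect already present at the Day 1 entry. The between-arm difference in change then estimates (1 − f) times the Day 5 effect:
- f = 0 (entry before the first drop, or no difference between arms yet): no distortion.
- f = 0.25 or 0.50: 0.75 or 0.50 of the effect. With d = 1 and r = 0.5 between Day 1 and Day 5, power falls from 75% to 51% or 26%.
- f < 0 (active drops less comfortable than vehicle on Day 1): the effect is overstated.

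The documents do not give f, or even its sign.

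**The case against.** A reader might infer that no symptom information is taken at Visit 1, that the log cannot be baseline-adjusted, and that change from Day 1 is biased toward zero. The documents do not support any of these.

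- The schedule does mark a patient comfort exam at Visit 1, and dispensing comes last in the section 7.2 list. A pre-dose patient rating may therefore be intended; the fault is that it is neither defined nor linked to the 1-5 score.
- The time of the Day 1 entry is unstated, not fixed as post-dose. An entry before the first drop fits the wording equally well.
- No passage plans a change-from-Day-1 analysis. Distortion would need a post-dose entry and arms that already differ, and it could go either way.
- Injection and discharge are graded before dispensing, so some pre-dose severity covariates exist whatever is done about symptoms.
- The power figures rest on assumed values. At r = 0.3 the gain is about four points, on a secondary endpoint with no stated hypothesis, in a trial of about 30 patients.

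All of this stands, and it confines the point to specification and precision. It does not remove the gap: an undefined row in a schedule, missing from both procedure lists, is not a specified baseline, and the grades of clinical signs are not on the symptom scale.

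**Conclusion.** The point holds as a gap in specification. The sole secondary endpoint has no defined pre-dose value, and the SAP does not say how the log will be analysed. Comparing Day 5 scores between randomised arms is valid without a baseline. What is forgone is precision: under a 1 SD effect and 15 per arm, power is 75% unadjusted against 79% to 96% with a pre-dose covariate at correlations of 0.3 to 0.7. Effect size and correlation are assumptions, and the gain is small if the correlation is low. No bias can be asserted from the documents. The primary endpoint and its 87% power are untouched. The change is worth making because it is cheap and a missed pre-dose score cannot be obtained later.

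**What to change.** 1. In the Visit 1 list of section 7.2, ahead of dispensing, add: *symptom score 1-5, recorded before the first drop*. Use the Day 1 slot of the comfort exam already in the schedule, and say that this exam is the 1-5 score.
2. State that the log entries, including Day 1, count as post-dose.
3. In the SAP, state that the Day 5 symptom score is compared between arms adjusted for the pre-dose score (for example, by ANCOVA).

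Cost: one line in section 7.2, short clarifications for the log and the comfort exam, one line in the SAP, and about a minute per patient. No extra visit or patients are needed. The downside is one more item on the Visit 1 form.

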4.3 Analysis Unit

The primary analysis will be performed on one eye of each subject. If both eyes qualify, the eye with the worse grade will be designated as the study eye. If both eyes have equal grade, the eye with more recent onset of symptoms will be designated as the study eye. If both eyes experienced onset of symptoms at the same time, the right eye will be designated as the study eye.

5.0 Trial Design

This is a Phase II single-center, double-masked, placebo controlled, randomized study of SCH1 for the treatment of infectious conjunctivitis. Approximately 30 subjects will be enrolled, who will be randomized in a 1:1 ratio between SCH1 and placebo. Subjects will be assessed at day 1, day 3, and day 5 for efficacy and safety.

5.1 Randomization and Masking

Approximately 30 patients will be randomized in a 1:1 ratio to either SCH1 or placebo. Randomization will be administered through “block randomization” (blocks of 4). The code will be kept by DR, who will not be involved in examining or grading patients.

Each investigator will receive a sealed envelope containing the description of the study medication assigned to each patient number. Investigators will be instructed not to open the envelope unless a medical emergency requires identification of the study medication.

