5.2 Treatments

The test article consists of one 3mL bottle of SCH1 ophthalmic suspension. Doses will be administered directly from the bottle. See section 8.0 for storage, handling and administration. The placebo, which consists of the vehicle for SCH1, will be supplied in an identical 3mL bottle the placebo will.

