8.0 Study Treatment

DR will provide SCH1 (the study drug) and identically packaged placebo (vehicle only). The SCH1 test article is an eyedrop suspension.

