8.3 Compliance

Compliance will be assessed by maintaining adequate drug dispensing and return logs. Patients will also keep written record of when treatments were given.

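### Section 5.1 prints one fixed block size of 4 in an unstratified single-centre trial with subjectively graded entry and outcome; undisclosed, randomly varying blocks would be a near-costless improvement

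*Combined protocol and SAP*

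**What the plan says.** Section 5.0 describes the design: "This is a Phase II single-center, double-masked, placebo controlled, randomized study of SCH1". Section 5.1 sets the allocation: "Approximately 30 patients will be randomized in a 1:1 ratio to either SCH1 or placebo", in blocks of a single stated size. No strata are described, so there is in effect one sequence.

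Section 5.1 also gives two safeguards. The first is an independent code holder, introduced directly after the block size: "blocks of 4). The code will be kept by DR, who will not be involved in examining or grading patients". The second is emergency envelopes: "Each investigator will receive a sealed envelope containing the description of the study medication assigned to each patient number". Investigators may open them only in a medical emergency that requires the treatment to be identified.

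Product matching is described in two places. Section 5.2 says "The placebo, which consists of the vehicle for SCH1, will be supplied in an identical 3mL bottle", and the sentence then breaks off in the text available. Section 8.0 says "DR will provide SCH1 (the study drug) and identically packaged placebo (vehicle only). The SCH1 test article is an eyedrop suspension". Neither section says whether the two liquids look alike. On handling of used product, section 8.3 says "Compliance will be assessed by maintaining adequate drug dispensing and return logs", without saying who receives the returned bottles.

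**The concern.** A permuted block protects allocation only while the block structure or the past assignments stay unknown. Here the structure is in the protocol, so protection rests on past assignments alone.

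This matters because of what is judged at the visits. The Synopsis makes entry depend on a grade of mild for injection and of mild or worse for discharge. Sections 7.1 and 7.2 set baseline grades at Visit 1. The primary endpoint in section 4.1 is built from the same 0-3 grades. The documents do not separate the person who enrols from the person who grades. If an assignment can be inferred, borderline enrolment decisions and borderline grades can drift by arm, and no later analysis can remove that. With about 15 patients per arm, a few grades can decide the result.

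**Working it through.** **Inputs.** Block size 4, ratio 1:1 and about 30 patients (5.1); single centre (5.0); twelve months of enrolment and five days of follow-up (5.3); cure rates of 20% and 80%, 15 per group, two-sided 0.05, Fisher's exact test, 87% power (SAP).

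**The plan's own figure.** Enumerating two binomials (n = 15 each, 0.20 and 0.80) and applying the two-sided Fisher test gives power 0.872. The SAP's 87% reproduces. The documents give no figure for predictability of allocation.

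**One treatment known.** A block of 4 holds two of each arm. Once one patient's arm is known, three places remain, two of them in the opposite arm. Each other patient is therefore in the opposite arm with probability 2/3. On average (3 + 2 + 1 + 0)/4 = 1.5 of those patients come later in the block.

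**Worst case: all earlier treatments recognised, block boundaries known.** There are 6 equally likely sequences.
- The 4th assignment is always certain. The 3rd is certain when the first two are alike (2 of 6 sequences). Expected certain per block: 1 + 1/3 = 4/3 of 4.
- Best-guess success at positions 1 to 4 is 1/2, 2/3, 2/3 and 1, a sum of 17/6 of 4 (70.8%).
- Thirty patients make 7 full blocks plus 2. Certain: 7 × 4/3 + 0 = 9.3 (31%). Correct guesses: 7 × 17/6 + 7/6 = 21.0 (70%), against 15 (50%) by chance.

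**Partial recognition.** Certainty needs both patients of one arm in the block to be recognised. If each earlier treatment is recognised independently with probability q, the certain share of a full block is q²/3. The guess rates come from enumeration.

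| q | certain, per full block | guessed correctly |
|---|---|---|
| 1 | 33% | 71% |
| 0.75 | 19% | 65% |
| 0.50 | 8% | 60% |
| 0.25 | 2% | 55% |

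**Randomly varying blocks of 4 and 6.** Assume equal chance of each size, and an observer who knows every past treatment and the two possible sizes but not their order. Updating the probabilities patient by patient over 20,000 simulated lists gives about 6% certain (5.7%, or 1.7 of 30) and 69% guessed correctly.

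**Timing.** 365/30 is about one enrolment every 12 days. An earlier patient would usually finish before the next one enrols, so anything learned could come in time.

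**Sensitivity of the result.** At 12/15 against 3/15 cured, Fisher p = 0.003; at 10/15 against 3/15, p = 0.025; at 9/15 against 3/15, p = 0.060. Near the threshold, one patient changes the conclusion.

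**Cost in balance.** Thirty is not a multiple of 4, so fixed blocks already give 16:14 with probability 1/3. With blocks of 4 and 6, the unfinished block at exactly 30 holds 0, 2 or 4 patients, so 16:14 is again the worst split. A difference of 3 in an unfinished block of 6 needs an odd total. Fisher power is 0.872 at 15:15 and 0.893 at 16:14.

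**The case against.** A reader might infer that anyone who recognises one earlier treatment can work out later assignments. That does not follow: one known treatment gives odds of 2/3, and certainty needs both allocations of one arm.

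A reader might also infer that the placebo visibly differs because SCH1 is a suspension and placebo is its vehicle. The documents do not say so. Section 5.0 calls the trial double-masked, and the sentence in 5.2 breaks off just after the bottle is matched. Silence about appearance is a gap in the description, not evidence of a difference. Nor do the documents say that graders see returned bottles: patients instil the drops themselves (8.2), and the code holder coordinates central storage and package delivery (8.1).

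It can further be said that block size is secondary. If the contents were recognisable, the current patient's arm would be exposed at any block size; if they are not, a block of 4 reveals little. Section 6.4 does not require unmasking for rescue, so emergency unmasking may be rare, and each one affects on average 1.5 later patients.

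All of this stands, and it limits the size of the problem. It does not supply a reason to print a single fixed size. Neither safeguard in 5.1 hides that size, and 5.1 itself permits one route by which a treatment becomes known even if the contents match perfectly.

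**Conclusion.** The point holds as a cheap improvement to the allocation method; it does not show that masking fails. Established from the documents: one fixed, printed block size, a single unstratified sequence, subjective grades for entry and outcome, and no statement that the size is withheld.

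The leak that needs no assumption about appearance is 2/3 odds for the rest of a block after an emergency unmasking. The 31% certain and 70% guessed are upper limits. They assume that every earlier treatment is recognised and the block boundaries are known, and the certain share falls with the square of the recognition rate. A visible difference between vehicle and suspension, and graders' access to returned bottles, are both assumptions.

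**What to change.** **Main change.** In 5.1, replace the fixed size with permuted blocks of randomly varying size. State that the sizes are held only by the code holder, and leave them out of the protocol given to those who enrol or grade. The gain is mainly the removal of certain assignments, since the best-guess rate stays near 69%. The cost is a regenerated list and one changed sentence, with a possibly slightly larger final imbalance and negligible effect on power. No patients, visits or staff are added.

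**Secondary clarification.** Complete the sentence in 5.2 to say whether the contents match in appearance. In 8.3, have returned bottles go back closed to the drug-supply role and not to the grader. Wrapping the bottles would not be enough, because it does not hide the drop from the patient, who instils it and also supplies the symptom score.

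Parts of the SAP are in the past tense. If enrolment is already complete, the list cannot be changed. The report should then state who knew the block size, whether any envelope was opened and how the contents compared.
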